 initiated at a total daily dosage of 10 mg/kg per day.

Study design:

Type of the study: randomized controlled study.

The following data will be gathered and evaluated for all patients:

I-before intervention:

- Serum creatinine, Creatinine clearance. .1
- 24 hour urine protein, urine protein/creatinine ratio. .2
 - Urine analysis. .3
 - HBA1c. .4
 - HGB. .5
 - Uric acid and lipid profile. .6
 - Lupus serology. .7

II-after intervention: All patients will be evaluated monthly regarding:

- Serum creatinine, creatinine clearance. .1
- 24 hour proteinuria, protein/creatinine ratio. .2
- Fasting, random and postprandial glucose levels. .3
 - CNI trough level if used. .4
 - Urine analysis. .5
 - HGB level. .6
 - Uric acid, lipid profile. .7
 - Lupus serology. .8

Cardiovascular assessment: .9

ECCHO.

Atherosclerosis and vascular calcification incidence (NCCT model).

Regular measurement of blood pressure each visit.

Outcomes:

- Effect of dapagliflozin compared to placebo on eGFR. .1
- Effect of dapagliflozin compared to placebo on systolic/diastolic blood .2 pressure.
 - Effect of dapagliflozin compared to placebo on body weight. .3
- Safety of dapagliflozin vs. placebo the number of hypoglycemia .4 episodes between groups and serious adverse events.

Statistical Analysis:

Qualitative data were displayed in cross tabulations, and quantitative data were described in terms of arithmetic mean ± SD. Bivariate techniques were used for initial evaluation of contrasts. Thus, the chi-square and Fisher's exact tests were used for comparisons of frequencies of qualitative variables; the Mann-Whitney test and the unpaired t-test were used for comparisons of means of two quantitative variables. A p-value <0.05 was considered significant. Graft and patient survival rates were assessed using the Kaplan-Meier method. All analyses were carried out using the computer package SPSS for windows, release 16 SPSS Inc. Chicago, III, USA.

Administrative design •

Informed consent will be obtained from all subjects and the approval will be obtained from institutional review board (IRB) in Faculty of Medicine, Mansoura University. There is no funding.

Research question

The main research question is: Does use of SGLT2i will show superiority over conventional lines of treatment of lupus nephritis patient as regard efficacy and safety.

Rationale and justification

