Statistical Analysis Plan

Document Control

Title: Statistical Analysis Plan for the Study of SGLT2 Inhibitors in Lupus Nephritis Patients

Protocol ID: [NCT05748925] Version: 1.0 Date: [11/3/2024] Principal Investigator: [[name]] Statistician: [[name]] Approval Signatures: Principal Investigator: [name] Statistician: [name]

Table of Contents

- 1. Introduction
- 2. Study Design
- 3. Study Objectives
- 4. Endpoints
- 5. Sample Size Justification
- 6. Statistical Methods
- 7. Handling of Missing Data
- 8. Interim Analysis
- 9. Safety Analysis
- 10. Data Quality and Management
- 11. Software
- 12. Appendices

1. Introduction

• **Purpose of the SAP**: This document outlines the statistical approach for analyzing data from the clinical trial studying the effects of SGLT2 inhibitors on renal, cardiovascular, and hematological outcomes in lupus nephritis patients.

2. Study Design

Design: Randomized, double-blind, placebo-controlled clinical trial.

Study Duration: Conducted from September 2022 to November 2023

Randomization: Patients were randomly assigned to either dapagliflozin (10 mg once daily) or placebo groups using computer-generated random tables in a 1:1 ratio stratified by age and gender.

Blinding: The study was double-blinded, and all trial staff and participants remained unaware of individual treatment assignments until study completion.

3. Study Objectives

Primary Objective: To evaluate the impact of SGLT2 inhibitors on renal, cardiovascular, and hematological parameters in lupus nephritis patients.

Secondary Objective: To explore changes in body weight, BMI, and other echocardiographic and iron profile parameters over 12 months.

4. Endpoints

Primary Endpoints

Renal Function: Serum creatinine, eGFR, and 24-hour urine protein

Cardiovascular Health: BNP levels and coronary calcification via NCCT

Hematological Parameters: Hemoglobin and erythropoietin levels

Hepcidin Level: Measured before and after intervention

Secondary Endpoints

Body Weight and BMI: Assessed at baseline and follow-up visits.

Echocardiographic Findings: Assessed pre- and post-intervention.

Iron Profile: Serum ferritin and TSAT

5. Sample Size Justification

Calculation: A sample size of 100 patients was targeted, accounting for potential dropouts, to provide sufficient power (80%) at a significance level of 0.05 to detect differences between the two groups.

6. Statistical Methods

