
General Considerations

Significance Level: A two-sided alpha level of 0.05 will be used for all primary analyses.

Analysis Populations:

Intent-to-Treat (ITT): All randomized patients will be analyzed according to their assigned group.

Per-Protocol (PP): Only patients completing the study without major protocol violations.

Primary Endpoint Analysis

Renal Outcomes: ANOVA for repeated measures for serum creatinine and eGFR if normally distributed, and the Friedman test for non-normally distributed data. Post-hoc tests using Bonferroni correction.

Cardiovascular Outcomes: Mann-Whitney U test for BNP levels and coronary calcification between groups.

Hematological Outcomes: Paired t-test for hemoglobin and erythropoietin levels if data is normally distributed; otherwise, Wilcoxon signed-rank test.

Secondary Endpoint Analysis

Body Weight and BMI: Compared over time using ANOVA for repeated measures.

Echocardiographic Parameters: Analyzed with paired t-tests, adjusted with Bonferroni correction.

Iron Profile: Analyzed pre- and post-intervention using ANOVA or Kruskal-Wallis for non-normally distributed variables.

Categorical Variables

Chi-Square Test: For between-group comparisons of categorical data (e.g., presence of diabetes, hypertension).

7. Handling of Missing Data

Imputation: Last observation carried forward (LOCF) for data missing at random; multiple imputation for extensive missing data.

Sensitivity Analysis: Conducted to evaluate the robustness of primary endpoint findings against different missing data assumptions.

8. Interim Analysis

Timing: An interim analysis is planned at the halfway point (6 months).

Stopping Rules: An O'Brien-Fleming approach will be applied to adjust the significance threshold for interim testing, allowing for an earlier stop for efficacy or safety concerns.

9. Safety Analysis

Adverse Events (AEs): Summarized by type, frequency, and severity. Fisher's exact test will be used to compare AE rates between groups.

Specific Safety Parameters: Monitoring for hypotension, electrolyte imbalances, and kidney function.

10. Data Quality and Management

Data Quality Measures: Includes data verification, regular audits, and query resolution.

Database Lock: Data will be locked and verified prior to the final analysis.

11. Software

Statistical Software: All analyses will be conducted using SPSS (Version 25).

12. Appendices

	Control group. (n= 41)	Study group. (n= 38)	P value

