Cholesterol mg/dL mean ± SD	185 ± 46	172 ± 40.7	0.5
Albumin (g/dL) mean ± SD	3.7 ± 0.4	3.7 ± 0.3	0.4
Random blood sugar (mg/dL) Median (min, max)	89 (66, 568)	92.5 (64, 243)	0.4
Uric acid (mg/dL) mean ± SD	6.2 ± 2.1	6.5 ± 1.7	0.2
Alanine aminotransferase (IU/L) Median (min, max)	17 (2, 84)	17 (7, 82)	0.8
Aspartate aminotransferase (IU/L) Median (min, max)	21(9, 66)	19 (12,72)	0.4
Sodium (mEq/L) mean ± SD	137 ± 3.1	136 ± 3	0.5
Potassium (mEq/L) mean ± SD	3.9 ± 0.4	4 ± 0.4	0.3

eGFR: estimated glomerular filtration rate; (Student T test or Mann-Whitney) for continuous data, and chisquare test for categorical data. Continuous data are expressed as mean (SD) or median (minimum – maximum). Categorical data are expressed as number (percentage). Level of significance < 0.05.

Table (4): Baseline hematological findings:

	Control group. (n= 41)	Study group. (n= 38)	P value		
Hemoglobin (g/dL) Mean \pm SD	11.9 ± 1.9	11.7 ± 1.7	0.5		
MCV (FL) Mean ± SD	82 ± 7	84 ± 6.9	0.9		
MCH (Pg) Mean ± SD	25.4 ± 2.9	26.3 ± 2.9	0.9		
Ferritin (mg/dL) Median (min, max)	60 (13, 1113)	33.5 (3, 1460)	0.09		
TSAT (%) Median (min, max)	23.8 (7, 64)	18 (6, 74)	0.05		
Erythropoietin level (IU/L) Mean ± SD	11.6 ± 2.1	11.3 ± 1.4	0.1		
Hepcidinlevel(ug/L) $Mean \pm SD$	198 ± 74	182 ± 76	0.3		
Platelet count (*10 ³) Mean \pm SD	288 ± 71	300 ± 79	0.7		

McW Mean corpuscle volume; MCH: Mean corpuscular hemoglobin; TSAT: Transferrin saturation test; (Student T test or Mann-Whitney) for continuous data, and chi-square test for categorical data. Continuous data are expressed as mean (SD) or median (minimum – maximum). Categorical data are expressed as number (percentage).; Level of significance < 0.05.

Table (5): Baseline Cardiac evaluation:

Control group. Study group. P value

	(n= 41)	(n= 38)	
Coronary calcification No. (%)	3 (7.3%)	11 (28.9%)	0.012
Coronary calcification severity No. (%) - No - Minimal - Mild - moderate	38 (92.7%) 1 (2.4%) 1 (2.4%) 1 (2.4%)	27 (71.1%) 3 (7.9%) 7 (18.4%) 1 (2.6%)	0.04
BNP (ng/L) Median (min, max)	52 (40, 557)	52 (34, 90)	0.8
Echocardiographic	c finding		0.6
EF % Mean \pm SD	65.4 ± 9.3	64.6 ± 5.4	0.6
LAD (ml) Mean ± SD	24.2 ± 7.6	24.9 ± 7.6	0.6
Aortic diameter (ml) Mean ± SD	24.7±7.4	24.8±7.1	0.9
ESV (ml/m) Median (min, max)	38±13.6	41±13.9	0.4
EDV (ml/m) Mean ± SD	98±35.7	111.5±31.6	0.08

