	P value**	0.5	0.7	0.7	0.3	0.6	
MCV (FL) Mean ± SD	Control	82±7	83±7	84±7	84.6±7.9	81.5±13	0.1
	Study	84±6.9	80±14	83±10	83.2±10.8	84±7	0.3
	P value**	0.9	0.1	0.5	0.5	0.4	
MCH (Pg) Mean ± SD	Control	25.4±2.9	27.3±9.8	28.5±9	26.9±3.2	26.9±3.1	0.08
	Study	26.3±2.9	27.3±9.5	27±3	26.6±3.5	27.1±3.4	0.8
	P value**	0.9	0.9	0.4	0.4	0.5	

(*) Within group analysis (repeated measure ANOVA).

(**) Between group analysis (Student T test or Mann-Whitney) for continuous data, and chi-square test for categorical data. Continuous data are expressed as mean (SD) or median (minimum – maximum). Categorical data are expressed as number (percentage).

MCV: Mean corpuscle volume; MCH: Mean corpuscular haemoglobin.

Table (8): other hematological findings differences between both groups:

	Grouping	Baseline	12 months	P value*
Ferritin (mg/dL)	Control	60 (13, 1113)	75 (6, 2127)	0.5
Median (min, max)	Study	33.5 (3, 1460)	64 (3, 1311)	0.8
	P value**	0.09	0.4	
TSAT (%) Median	Control	23.8 (7, 64)	28 (5, 62)	0.1
	Study	18 (6, 74)	20 (6, 66)	0.9
	P value**	0.05	0.1	
Erythropoietin	Control	11.6±2.1	12.8 ± 3.5	0.08
SD	Study	11.3±1.4	12.4 ± 3.5	0.1
	P value**	0.1	0.6	
Hepcidin level ug/L	Control	198 ± 74	128 ±63	0.001
Mean ± SD	Study	182±76	116±15	0.001
	P value**	0.3	0.2	
Platelet count	Control	288 ± 71	283 ± 74	0.6
(×10³) Mean ± SD	Study	300 ± 79	276 ± 65	0.01
	P value**	0.7	0.5	

(*) Within group analysis (paired t test).

(**) Between group analysis (Student T test or Mann-Whitney) for continuous data, and chi-square test for categorical data.

Continuous data are expressed as mean (SD) or median (minimum – maximum). Categorical data are expressed as number (percentage).

TSAT: Transferrin saturation test

Table (9): Cardiac evaluation differences between both groups after 12 months:

	Control group	Study group	P value
Coronary calcification No. (%)	1 (2.4%)	11 (28.9%)	0.001
Coronary calcification severity No. (%) - No - Minimal - Mild - moderate	40 (97.6%) 0 0 1 (2.4%)	27 (71.1%) 9 (23.7%) 2 (5.3%) 0	0.002
BNP ng/L Mean \pm Sd	66 ± 22.1	65.8±21	0.9
Echocardiographic findi	ng		
EF % Mean ± SD	65.5±5.8	64.9±5.2	0.8
LAD ml Mean \pm SD	26.7±7.6	28.2±8.6	0.4
Aortic diameter ml Mean ± SD	26.6±6.5	25.5±6.2	0.4
ESV ml/min Mean ± SD	39.5±18	36.3±9.3	0.3
EDV ml/min Mean ± SD	108±29.6	109±19.3	0.9

BNP: Brain natriuretic peptide; EF: Ejection fraction; LAD: Left atrial dimension; ESV: End- systolic volume; EDV:

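### The Table 9 p-values for coronary calcification cannot support a treatment conclusion: most of the arm difference predates treatment, and at least 8 of 14 calcified patients were graded lower at 12 months without explanation

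*SAP*

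**What the plan says.** SAP section 4 lists among the primary endpoints "Cardiovascular Health: BNP levels and coronary calcification via NCCT". SAP section 6 gives the analysis: "Cardiovascular Outcomes: Mann-Whitney U test for BNP levels and coronary calcification between groups". No baseline term, change score or restriction by baseline status is mentioned. The same section sets the test level: "A two-sided alpha level of 0.05 will be used for all primary analyses". The protocol's cardiovascular assessment names the outcome as "Atherosclerosis and vascular calcification incidence (NCCT model", which points to new cases.

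SAP section 12 reports the grades in the order none, minimal, mild, moderate. Baseline (Table 5) is "38 (92.7%) 1 (2.4%) 1 (2.4%) 1 (2.4" per cent in the control arm and "27 (71.1%) 3 (7.9%) 7 (18.4%) 1 (2.6" per cent in the study arm. At 12 months (Table 9) the control arm reads "40 (97.6%) 0 0 1 (2.4" per cent and the study arm 27, 9, 2, 0. The printed p-values are 0.012 (any calcification) and 0.04 (severity) at baseline, and 0.001 and 0.002 at 12 months.

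Neither document gives grade cut-offs, a calcium score, the number of readers, or any paired or repeat reading. SAP section 10 promises data verification and audits in general terms only.

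**The concern.** Two features of these tables make the 12-month p-values hard to read.

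First, the arms already differed in calcification before anyone was treated, and the planned test compares 12-month status as if they had not.

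Second, the grades fall in both arms. On placebo, three calcified patients become one. In the study arm, the number graded mild or moderate drops from eight to two. The documents offer no explanation.

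This is one of the few significant between-arm results in the appendix, and it can be read in opposite directions. The unadjusted 12-month comparison points against dapagliflozin (11/38 v 1/41 calcified). A within-arm comparison of severity would point in its favour, and Tables 6 to 8 already print within-arm p-values for other outcomes. Both readings would rest on the same grades.

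**Working it through.** **Inputs.** Grades none/minimal/mild/moderate, from SAP Tables 5 and 9:

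| Arm | Baseline | 12 months |
|---|---|---|
| Control (n=41) | 38/1/1/1 | 40/0/0/1 |
| Study (n=38) | 27/3/7/1 | 27/9/2/0 |

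Table 9 prints no n, but its percentages fit 41 and 38 (40/41 = 97.6%; 27/38 = 71.1%).

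**Step 1: reproduce the printed p-values.** Pearson chi-square without continuity correction, N(ad−bc)²/(product of the four margins):
- Baseline, 3/41 v 11/38: 79 × (3×27 − 38×11)² / (41×38×14×65) = 79 × 337² / 1,417,780 = 6.33, p=0.012. Matches. Fisher's exact test gives 0.017.
- 12 months, 1/41 v 11/38: 79 × (1×27 − 40×11)² / (41×38×12×67) = 79 × 413² / 1,252,632 = 10.76, p=0.001. Matches. Fisher gives 0.0012.
- 12-month severity: chi-square 0.0024, matching the printed 0.002. The Mann-Whitney test named in SAP section 6 gives 0.0016.
- Baseline severity, printed 0.04: chi-square 0.064, likelihood ratio 0.049, Mann-Whitney 0.014. None of these gives 0.04.

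**Step 2: how much of the difference predates treatment.**
- Baseline: 28.9% − 7.3% = 21.6 points.
- 12 months: 28.9% − 2.4% = 26.5 points.
- The remaining 4.9 points are the net fall of two control patients (2/41). The study count is 11 at both times.
- Putting those two control patients back to their baseline grades gives 3/41 v 11/38 again: chi-square 0.012, Fisher 0.017. On severity, Mann-Whitney gives 0.019 and chi-square 0.023. The comparison stays significant.

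**Step 3: minimum number graded lower.** If the count at or above a grade falls by k, at least k patients moved down across that grade.
- Control, minimal or worse: 3 to 1, so at least 2 of 3.
- Study, mild or worse: 8 to 2, so at least 6 of 11. Exactly 6 requires the moderate patient to drop two grades or more; if that patient dropped only one, the minimum is 7.
- Total: at least 8 of 14 (57%). A search over all transition tables that fit these margins gives the same minima and shows that no upgrade is needed in either arm.
- Minimum rates of 2/3 and 6/11 give Fisher p=1.0, so these minima show no arm difference in downgrading.

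**Step 4: why a simple change analysis is not safe either.** Only patients who start calcified can move down: 11 in the study arm, 3 in control. Under minimum movement (6 down, 0 up), a two-sided sign test within the study arm gives 2 × (1/2)⁶ = 0.031; control (2 down, 0 up) gives 2 × (1/2)² = 0.5. A reading shift common to both arms would therefore look like regression on drug alone.

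**Step 5: what the tables leave unknown.** New calcification among those free of it at baseline could be 0 or 1 of 38 in control and anything from 0 to 11 of 27 in the study arm. The printed counts fit no new cases at all, and equally fit 11/27 (41%) against 0/38.

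**The case against.** A reader might infer that the grading is not reproducible and that reading error produced the significant arm difference. The documents do not support either step.

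- No scan is reported as read twice, so reproducibility was not measured. Readings 12 months apart cannot separate reading error from real change.
- The difference was significant before treatment and stays so with the two control patients restored. With the study arm at 11, Fisher's test remains below 0.05 up to 4/41 control positives (p=0.044) and passes it only at 5/41 (p=0.093).
- The SAP states that "all trial staff and participants remained unaware of individual treatment assignments until study completion". Misreading that is equal in both arms does not inflate false positives: at common positive rates from 0.05 to 0.25, the exact type I error of the 41 v 38 comparison is 0.040 to 0.052 for chi-square and 0.018 to 0.036 for Fisher. Reading that differed by arm could inflate it, but nothing shows that it occurred.
- Six of the eight minimum downgrades are on dapagliflozin, where change is the question under test. The placebo evidence is two patients, and controls were not untreated: 73.2% took statins and 63.4% ACEI/ARBs at baseline.
- A reporting slip is a live alternative. In Table 2, as extracted, the class V counts do not match their percentages, and aspirin is 18 (34.4%) although 18/38 = 47.4%.

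All of this stands. It removes the causal claim about reading error. It does not make the unadjusted 12-month p-value interpretable, and it adds a reason to check the tables against source.

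**Conclusion.** The unadjusted 12-month comparison of this primary endpoint cannot be read as a treatment effect. Of the 26.5-point difference, 21.6 points were present at baseline; the net fall of two control patients moves the printed p-value from 0.012 to 0.001. In addition, at least 8 of the 14 patients calcified at baseline (2 of 3 control, 6 of 11 study) were graded lower, for reasons the documents do not give.

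The count of 8 assumes that the same 41 and 38 patients were read at both times.

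Two further readings are tempting and unsupported: that dapagliflozin promotes calcification (the study count did not change), and that it reduces severity (grades also fell on placebo). The point should be addressed before any calcification result is reported.

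**What to change.** 1. **SAP section 6.** Replace the unadjusted 12-month comparison with one that uses each patient's own baseline grade. Report new calcification only among the 65 patients calcium-free at baseline (38 control, 27 study), and show the baseline-by-12-month grade cross-table for each arm. This needs only data already collected and fits the protocol's interest in incidence. The SAP already contains results, so label the analysis as specified after they were known.
2. **SAP section 10.** Check Tables 5 and 9 against source records, including the baseline severity p-value of 0.04, and state how the scans were graded. If the scans are stored and a reader is available (the documents state neither), have each patient's two scans re-scored together, masked to arm and scan order. Start with patients calcified on either scan: 3 to 4 control plus 11 to 22 study, so 14 to 26 patients.
3. **Reporting.** Draw no treatment conclusion from the Table 9 calcification p-values until this is done.

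The cost is some checking and, where possible, some reading time. The printed p=0.001 may not survive.

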End diastolic volume; Chi square test; Student t- test; Man, Whitney test; Level of significance < 0.05.

Table (10): Comparison between both groups as regard post intervention side effects

	Control group. (n= 41)	Study group. (n=38)	P value
AKI episodes No. (%)			
- No	38 (92.7%)	31 (81.6%) 5 (13.2%)	0.17
- once	1 (2.4%) 2 (4.9%)	2 (5.3%)	
- twice			
UTI No. (%)			
- No	35 (85.4%) 4 (9.8%)	31 (81.6%) 5 (13.2%)	0.8
- once	2 (4.9%)	2 (5.3%)	
- more than once			
Gynecological infection No. (%)	1 (2.4%)	2 (5.3%)	0.6
Viral infection No. (%)	1(2.4%)	1 (2.6%)	1
MMF intolerance No. (%)	1 (2.5%)	2 (5.3%)	0.6
Renal biopsy No. (%)	2 (4.9%)	1 (2.6%)	0.6
Increase steroid dose No. (%)	7 (17.1%)	4 (10.5%)	1

UTI: urinary tract infection episodes; AKI: acute kidney injury; chi-square test for categorical data. Categorical data are expressed as number (percentage).; Level of significance < 0.05.

figure1: flow chart of participating populations

Figure (2) shows difference between individual which had improved eGFR or not as regard to their basal eGFR in total cohort, which found that improving eGFR had been occurred in patients with lower eGFR (107±50 vs 137±58 ml/min/m²

Figure (3) show no significant difference between the drug and placebo groups (p=0.857). as regard incidence of anemia before intervention, the drug group has 23 anemic participants (60.5%) versus 24 participants (58.5%) in the placebo group, while post intervention, In the anemia category, the drug group has 16 participants (42.1%), while the placebo group has 22 participants (53.7%) with non-significant differences (p = 0.3)

Figure (4) differences in body weight between both groups at different time points:

Glossary of Terms and Abbreviations

AA	Amino Acids
ABIN	A20 Binding Inhibitor Of NF-Kb
ACE	Angiotensin-Converting Enzyme Inhibitors
ACR	American College of Rheumatology
AKI	Acute Kidney Injury
ALCAM	Activated Leucocyte Adhesion Molecule
ALP	Alkaline Phosphatase
AMP	Adenosine Monophosphate
АМРК	Amp-Activated Protein Kinase
ANA	Antinuclear Antibodies
ANG II	Angiotensin 2
ANOVA	Analysis Of Variance
ANTI-DSDNA	Anti Double Stranded Deoxyribonucleic Acid
	Antibodies
ANTI-SM	Anti-Smith Antibodies
APLS	Antiphospholipid Syndrome
ARBS	Angiotensin 2 Receptor Blockers
ATN	Acute Tubular Necrosis
ATP	Adenosine Triphosphate
BAFF	B-Cell-Activating Factor
BLISS	B Lymphocyte Stimulator Inhibitor Belimumab
	Plus Standard Therapy
BMI	Body Mass Index
BNP	Brain Natriuretic Peptide
BP	Blood Pressure

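### SAP Figure 2 infers that eGFR improves in patients with lower baseline eGFR, from a pooled comparison in which regression to the mean would make improvers start lower anyway

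*SAP*

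**What the plan says.** The text for Figure 2 in SAP section 12 says that the figure "shows difference between individual which had improved eGFR or not as regard to their basal eGFR in total cohort". It then states the result, "which found that improving eGFR had been occurred in patients with lower eGFR", with baseline values of 107±50 vs 137±58. The extracted text gives no cut-off for improvement, follow-up time, group sizes, p-value, split by arm or caveat. The figure itself was not available for review.

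SAP section 6 plans no analysis of improvers against non-improvers. For the renal endpoints it names "ANOVA for repeated measures for serum creatinine and eGFR if normally distributed", with the Friedman test as the alternative. Table 6 shows mean eGFR falling from baseline to 12 months in both arms: 114±51 to 100.3±44.5 in control (n=41) and 128±59.7 to 115.7±48 in the study group (n=38). The between-group p-values across the five visits run from 0.2 to 0.9.

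**The concern.** Patients are grouped by change from baseline and then compared on that same baseline. A patient whose baseline reading happened to be low for them is more likely to read higher later, and so to count as improved. One whose baseline happened to be high is more likely to count as not improved. Improvers will therefore tend to have the lower baseline without any treatment effect or true change. Any cut-off on change from baseline has this coupling, so the point does not turn on how improvement was defined.

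Pooling the arms also means that the comparison, as described, says nothing about dapagliflozin against placebo. eGFR is listed among the primary endpoints, and Table 6 shows no between-arm difference in it. Figure 2 is the one place in the appendix text where eGFR is said to improve and the patients concerned are characterised. A reader could carry away a marker of who improves that the analysis cannot establish.

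**Working it through.** **Inputs.** Arm sizes and eGFR means and SDs at baseline and 12 months come from SAP Table 6; the group means and SDs come from the Figure 2 text. The correlation r between baseline and follow-up is in neither document and is varied from 0.5 to 0.95. Improvement is taken as any rise above baseline; where Table 6 follow-up values are used, the time point is taken as 12 months. Both are assumptions.

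**Step 1: is Figure 2 consistent with Table 6?**
- Pooled baseline mean = (41×114 + 38×128)/79 = 120.7.
- Pooled baseline SD = √{[40×51² + 37×59.7² + 41×(114−120.7)² + 38×(128−120.7)²]/78} = 55.4.
- The same formulas at 12 months give 107.7 and 46.6, so the mean change is −13.0 (−13.7 control, −12.3 study).
- For 107 and 137 to average 120.7, the improver share must be (137−120.7)/30 = 0.54, about 43 of 79. With 43 and 36 patients, 107±50 and 137±58 recombine to 120.7, SD 55.5.

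Figure 2 thus fits the whole cohort. The group means themselves cannot be reproduced without patient-level data.

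**Step 2: expected gap without a drug effect.** Let B be baseline, F follow-up and D = F − B, jointly normal, with improvement meaning D > 0. Write d for the mean of D, s_D for its SD, p = P(D > 0) and φ for the standard normal density. Then

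gap = s_B × corr(B,D) × φ(d/s_D) / [p(1−p)], with corr(B,D) = (r·s_F − s_B)/s_D.

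With equal SDs, corr(B,D) = −√((1−r)/2), which is negative for every r below 1.

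*No true change, SD 55.4 at both times.* Here p = 0.5 and the gap is −4 × 0.399 × 55.4 × √((1−r)/2). At r = 0.8 this is −4 × 0.399 × 55.4 × 0.316 = −28. A gap of −30 is expected at r of about 0.77.

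*Table 6 values (SD 55.4 to 46.6, mean change −13.0).* At r = 0.8, s_D = 33.3, corr(B,D) = −0.546, p = 0.35 and φ = 0.370. The gap is 55.4 × (−0.546) × 0.370/(0.35×0.65) ≈ −49, or about 89 vs 138.

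| r | Equal mean and SD | Table 6 mean and SD |
|---|---|---|
| 0.5 | −44 | −56 |
| 0.6 | −40 | −53 |
| 0.7 | −34 | −51 |
| 0.8 | −28 | −49 |
| 0.9 | −20 | −51 |
| 0.95 | −14 | −58 |

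The placebo arm's figures alone (51 to 44.5, change −13.7) give −41 to −49 over the same range. A lognormal version of the equal-SD case gives −42 to −13, so normality is not driving the result.

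**Step 3: a trial of this size.** Simulated trials of 79 patients with equal means and SDs and no true change (4,000 per row):

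| r | Gap negative | Gap −30 or beyond | p < 0.05 |
|---|---|---|---|
| 0.6 | 99.98% | 79% | 92% |
| 0.7 | 99.9% | 65% | 82% |
| 0.8 | 99% | 44% | 62% |
| 0.9 | 95% | 21% | 36% |

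A gap in the reported direction is almost certain under no effect, and a nominally significant one is common.

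**The case against.** The strongest reply is that the artefact has not been shown to produce the reported numbers. At r = 0.8 with equal means and SDs the model gives about 107 vs 135, and a reader might infer that regression to the mean reproduces the reported 107 vs 137. The documents do not support that. r is not reported, and Table 6 shows both the mean and the SD falling in both arms. With those values the model gives about 89 vs 138 and 35% improvers, whereas Figure 2 implies about 54%. A Pitman-Morgan test of equal variances on the pooled SDs gives p of about 0.03, 0.01 and 0.001 at r = 0.7, 0.8 and 0.9 (0.06 to 0.08 at r = 0.5 to 0.6). Some real, greater decline in patients with high baseline is therefore plausible. This objection stands as a limit on the size that can be attributed to the artefact. It does not make the comparison interpretable, because the figure cannot separate the two sources.

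A second reply is that the text describes the total cohort and credits nothing to dapagliflozin. That is right. A reader might infer a claim that patients with low eGFR benefit from the drug, but the SAP does not make it. Nor does the mean fall in both arms contradict a statement that some individuals improved. The fault is narrower: low baseline is presented as marking those who improve.

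Third, the figure is unavailable and the extracted text ends inside an open bracket, so a definition, p-value or arm split shown there cannot be excluded. The criticism rests on the conclusion stated in the text.

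**Conclusion.** The point holds as a criticism of the stated inference. Grouping by change and comparing on baseline produces the reported direction without any drug effect: for every r below 1 with equal SDs, and for every r with Table 6's SDs. Under no true change the expected gap is −44 to −14 for r from 0.5 to 0.95, which brackets the reported −30. With Table 6's mean and SD it is −49 to −58, larger than reported and possibly part real. Regression to the mean is a sufficient explanation of the direction. It is neither a proven sole cause nor a reproduction of the figure.

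The sizes rest on an assumed r, an assumed definition and time point for improvement, and approximate normality. The mismatch between the implied 54% improvers and the model's 35% may reflect skewed data or a different time point or cut-off, which is a further reason to define the term. Severity is minor to moderate, because no planned endpoint analysis depends on this figure.

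**What to change.** Either of two changes is enough for the figure:
- Remove the statement about which patients improved.
- Keep the figure as descriptive and post hoc, define improvement (cut-off and time point), give the group sizes, and state that regression to the mean is expected to produce a gap in this direction.

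If the question is who benefits from dapagliflozin, that is a different analysis. Fit 12-month eGFR on arm, baseline eGFR and the arm-by-baseline interaction, report the interaction with its 95% CI, and label it exploratory.

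The cost is an edited caption, or one regression on data already held. The downside is imprecision with 79 patients. As a rough guide, the residual SD at r = 0.8 is 46.6×√(1−0.64) = 28, and the SE of the slope difference is 28×√[1/(40×51²) + 1/(37×59.7²)] = 0.116. The 95% half-width is then 1.96×0.116×50, or about 11 eGFR units for a 50-unit difference in baseline (about 16 at r = 0.5 and 6 at r = 0.95). A wide interval should be reported as inconclusive.
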